8.3.2.1 Suspected

A suspected adverse reaction is defined as any adverse event for which there is a reasonable possibility that the drug caused the adverse event. For the purposes of IND safety reporting, “reasonable possibility” indicates that there is evidence to suggest a causal relationship between the drug and the adverse event. A suspected adverse reaction implies a lesser degree of certainty about causality than an adverse reaction.

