8.7 Expedited Reporting

Reporting to the Data and Safety Monitoring Committee

If a death occurs during the treatment phase of the study or within 30 days after the last administration of the study drug(s) and it is determined to be related either to the study drug(s) or to a study procedure, the Investigator or his/her designee must notify the DSMC Chair (or qualified alternate) within 1 business day of knowledge of the event. The contact may be by phone or e-mail.

Reporting to UCSF Institutional Review Board (IRB)

The Principal Investigator must report events meeting the UCSF IRB definition of “Unanticipated Problem” (UP) within 10 business days of his/her awareness of the event.

Expedited Reporting to the Food and Drug Administration

If the study is being conducted under an IND, the Investigator is responsible for determining whether or not the suspected adverse reaction meets the criteria for expedited reporting in accordance with Federal Regulations (21 CFR §312.32).

The Investigator must report in an IND safety report any suspected adverse reaction that is both serious and unexpected. The Investigator needs to ensure that the event meets all three definitions:

- Suspected adverse reaction
- Unexpected
- Serious

If the adverse event does not meet all three of the definitions, it should not be submitted as an expedited IND safety report.

The timeline for submitting an IND safety report to FDA is no later than **15 calendar days** after the Investigator determines that the suspected adverse reaction qualifies for reporting (21 CFR 312.32(c)(1)).

Any unexpected fatal or life-threatening suspected adverse reaction will be reported to FDA no later than **7 calendar days** after the Investigator’s initial receipt of the information (21 CFR 312.32(c)(2)).

Any relevant additional information that pertains to a previously submitted IND safety report will be submitted to FDA as a Follow-up IND Safety Report without delay, as soon as the information is available (21 CFR 312.32(d)(2)).

Reporting to Pharmaceutical Companies providing Study Drug

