Any serious adverse event occurring after the patient has provided informed consent and until 4 weeks after the patient has stopped study participation must be reported. This includes the period in which the study protocol interferes with the standard medical treatment given to a patient (e.g. treatment withdrawal during washout period, change in treatment to a fixed dose of concomitant medication). As soon as an Investigator becomes aware of an AE that meets the definition of “serious”, this should be documented to the extent that information is available. This includes serious, related, labeled (expected) and serious, related, unlabeled (unexpected) adverse experiences. All deaths during treatment or within 30 days following completion of active protocol therapy must be reported within 24 hours. Serious adverse events occurring more than 4 weeks after study discontinuation need only be reported if a relationship to the study drug (or therapy) is suspected.

Investigator shall notify the appropriate pharmaceutical company **within twenty-four (24) hours** of making such discovery by submitting the completed SAE report form and any other pertinent SAE information as indicated on the SAE reporting form. Applicable events will be reported to the IRB and FDA as per current policies.

This report must be submitted by Institution to the appropriate pharmaceutical company even if it is not felt to be drug related:

- [REDACTED]
 - [REDACTED]
 - [REDACTED]
- [REDACTED]
 - [REDACTED]
 - [REDACTED]
- [REDACTED]
 - [REDACTED]
 - [REDACTED]
 - [REDACTED]
 - [REDACTED]
- [REDACTED]
 - [REDACTED]
 - [REDACTED]
 - [REDACTED]
- For Comparator Drugs/Secondary Suspects (Concomitant Medications), all serious adverse experiences will be forwarded to the product manufacturer by the investigator.
- Pregnancy (for a subject or for the partner of a subject) that occurs during study participation, although not itself an SAE, should be reported. To ensure patient safety each pregnancy must also be reported to the appropriate pharmaceutical company within 24 hours of learning of its occurrence. The pregnancy should be followed up to determine outcome, including spontaneous or voluntary termination, details of birth, and the presence or absence of any birth defects, congenital abnormalities or maternal and newborn complications.

SAEs that must be recorded on an SAE Reporting form include the following:

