10.7 Oversight and Monitoring Plan

The UCSF Helen Diller Family Comprehensive Cancer Center DSMC will be the monitoring entity for this study. The UCSF DSMC will monitor the study in accordance with the NCI-approved Data and Safety Monitoring Plan (DSMP). The DSMC will routinely review all adverse events and suspected adverse reactions considered "serious". The DSMC will audit study-related activities to ensure that the study is conducted in accordance with the protocol, local standard operating procedures, FDA regulations, and Good Clinical Practice (GCP). Significant results of the DSMC audit will be communicated to the IRB and the appropriate regulatory authorities at the time of continuing review, or in an expedited fashion, as applicable. See Appendix 2 Data and Safety Monitoring Plan for a Phase 2 or 3 Institutional Study, for additional information.

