Adverse events reporting to the DSMC will include reports from both the UCSF Coordinating Center, as well as the participating sites. The DSMC will be responsible for monitoring all data entered in OnCore® at the UCSF Coordinating Center and the participating sites. The data (i.e. copies of source documents) from the participating sites

will be faxed over to the UCSF Coordinating Center prior to the monitoring visits in order for the DSMC to monitor the participating site's compliance with the protocol, patient safety, and to verify data entry.

Adverse Event Review and Monitoring

All grade(s) 3-5 adverse events, whether or not unexpected, and whether or not considered to be associated with the use of the study drug, will be entered into OnCore®, UCSF's Clinical Trial Management System.

All Grade 3-5 adverse events entered into OnCore® will be reviewed on a monthly basis at the UCSF Site Committee meetings. All clinically significant adverse events must be reported to the UCSF Coordinating Center by the participating sites within 10 business days of becoming aware of the event or during the next scheduled quarterly conference call, whichever is sooner. The UCSF Site Committee will review and discuss the selected toxicity, the toxicity grade, and the attribution of relationship of the adverse event to the administration of the study drug(s) from the UCSF Coordinating Center and the participating sites.

In addition, all suspected adverse reactions considered "serious" must be entered in OnCore® and reported to the UCSF Coordinating Center within 1 business day. The suspected adverse reactions considered "serious" will be reviewed and monitored by the Data and Safety Monitoring Committee on an ongoing basis and discussed at the DSMC meeting, which take place every six (6) weeks.

If a death occurs during the treatment phase of the study or within 30 days after the last administration of the study drug(s) and is determined to be related either to the investigational drug or any research related procedure, the Study Chair at the UCSF Coordinating Center or the assigned designee must be notified within 1 business day from the participating site(s) and the Study Chair must then notify the DSMC Chair or qualified alternate within 1 business day of this notification. The contact may be by phone or e-mail.

Increase in Adverse Event Rates

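### An SAE or death that a participating site judges unrelated is due at the drug company within 24 hours but can take up to 10 business days to reach the Coordinating Center

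*Combined protocol and SAP*

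**What the plan says.** **From site to Coordinating Center (Appendix 2, Adverse Event Review and Monitoring).** Serious suspected adverse reactions "must be entered in OnCore® and reported to the UCSF Coordinating Center within 1 business day". Deaths on treatment or within 30 days of the last dose have the same 1-business-day limit, but only if judged related to the investigational drug or a research procedure. For other events: "All clinically significant adverse events must be reported to the UCSF Coordinating Center by the participating sites within 10 business days of becoming aware", or at the next quarterly call, whichever is sooner. The plan does not define clinically significant.

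**What counts as suspected (8.3.2.1 and 8.4).** "A suspected adverse reaction is defined as any adverse event for which there is a reasonable possibility that the drug caused the adverse event". In the attribution table of 8.4, *possible* counts as related and *unlikely* as unrelated.

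**To the drug company (8.7).** SAEs are due within 24 hours of discovery. Of the SAE report the section says: "This report must be submitted by Institution to the appropriate pharmaceutical company even if it is not felt to be drug related". The same subsection wants all deaths on treatment or within 30 days reported within 24 hours, without a relatedness condition.

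**To the DSMC (8.6, 8.7, 10.7, Appendix 2).** A death on treatment or within 30 days goes to the DSMC Chair within 1 business day if "it is determined to be related either to the study drug(s) or to a study procedure". Sections 8.6 and Appendix 2 describe ongoing DSMC review of serious suspected reactions. Section 10.7 can be read as routine review of all adverse events.

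**To the FDA (8.7).** The rule begins "Any unexpected fatal or life-threatening suspected adverse reaction will be reported to FDA no later than"; the limit it then sets is 7 calendar days, counted from when the Investigator first receives word of the event.

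**The concern.** The fast route to the Coordinating Center depends on the site's own causality judgement; the fast route to the drug company does not. A site that labels a fatal event *unlikely* owes the company a report within 24 hours. It owes the Study Chair one only under the slower rule. Yet Section 8 and Appendix 2 make the Study Chair responsible for monitoring safety at all participating sites.

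This matters because no single site will see much. The front matter lists ten participating sites besides UCSF, and the trial uses four drugs and plans 44 patients (at most 50). Several events called unrelated on one drug, each at a different site, can be recognised as a pattern only centrally. These are the events for which central notice has no short deadline.

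**Working it through.** The plan gives no statistical figure to reproduce. The check sets the reporting rules side by side and converts business days to calendar days.

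**1. Routes for one event.** Take an SAE or on-treatment death that a participating site attributes as *unlikely*.

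| Recipient | Rule | Depends on attribution? | Limit |
|---|---|---|---|
| Drug company | 8.7 | No | 24 hours |
| Coordinating Center, fast route | Appendix 2 | Yes: suspected reaction or related death | Does not apply |
| Coordinating Center, remaining route | Appendix 2 | No | 10 business days, or next quarterly call if sooner |
| DSMC Chair, deaths | 8.7, Appendix 2 | Yes | Does not apply |

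No other section gives a faster fixed route from site to Coordinating Center for this event.

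**2. Calendar time, ignoring public holidays.**
- Ten business days is two working weeks: 14 calendar days when the site becomes aware on a weekday, 13 from a Saturday, 12 from a Sunday.
- One business day is 1 calendar day from Monday to Thursday or from a Sunday, 3 from a Friday and 2 from a Saturday.

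**3. Lag between company and Study Chair.** From a weekday, 14 − 1 = 13 days. From a Saturday, 13 − 1 = 12; from a Sunday, 12 − 1 = 11. These are ceilings: a site may report earlier, and a quarterly call may fall inside the window.

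**4. Patients per site and drug.** With UCSF there are 11 sites, and 11 × 4 = 44 site-by-drug cells. If patients were spread evenly (an assumption), that is 44/44 = 1.0 patient per cell, or 50/44 = 1.1 at the maximum enrolment.

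**5. The FDA limit.** The 7-day rule covers only unexpected fatal or life-threatening *suspected* reactions, so an event judged unrelated is outside it. Suppose central review on day 14 changes the attribution. If the clock ran from the site's awareness, the limit passed 14 − 7 = 7 days earlier. If it starts when the Coordinating Center is told, it expires on day 14 + 7 = 21 and nothing has been missed. Section 8.7 does not say whose receipt starts the clock. The 15-day limit runs from the determination that an event qualifies, so late site reporting alone cannot breach it.

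**The case against.** The strongest reply is that the plan has other central safeguards.

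- **OnCore entry.** Grade 3 to 5 events are entered whatever the attribution (8.4, Appendix 2). But the 1-business-day entry rule covers only serious suspected reactions; otherwise 10.6 asks for case report forms as soon as possible after the visit.
- **Central review of attribution.** A reader might infer that attribution is settled once, at the site. It is not: 8.6 and Appendix 2 have the Site Committee discuss attribution, and Appendix 2 extends this to events from participating sites. The review is monthly for grade 3 to 5 events (8.6 also describes a weekly review) and can only follow entry or notification.
- **DSMC access.** A reader might infer that the DSMC never sees unrelated events. Appendix 2 makes it responsible for monitoring all OnCore data, and 10.7 may be broader than 8.6. What is missing is prompt notification: monitoring is six-monthly, on 20% of subjects.
- **Rate trigger.** Appendix 2 requires the Study Chair to notify the DSMC if grade 3 or 4 events exceed the brochure or label rate, with no relatedness condition. This helps with patterns but does not cover deaths.

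Two further inferences go too far. The plan does not show that an FDA deadline would be missed, for the reasons in step 5. Nor is relatedness the only test before an expedited report: 8.7 also requires that the event be unexpected. Section 8.3.2.2 makes deaths anticipated from the disease unexpected, but events listed in the brochure at the observed specificity and severity remain expected.

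One objection stands as a limit. Section 8.7 assigns the company report to the Investigator or Institution without saying whether that is the site or UCSF, and the company-specific lines are redacted. If reports pass through UCSF, the Coordinating Center would learn of the event within the same 24 hours. The sentence on deaths names no recipient, although it stands in the subsection on drug companies.

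**Conclusion.** The mismatch is real: for an SAE or death judged unrelated, 24 hours to the company against up to 10 business days to the Coordinating Center. The company can be ahead of the Study Chair by up to about 13 calendar days. That figure assumes awareness on a weekday, no holidays, no earlier quarterly call, and a site that sends the company report itself. The safeguards reduce the consequence, but none sets a fixed prompt deadline for these events.

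The sections also disagree on what the DSMC receives, and no event-specific DSMC notification is required for a death judged unrelated. This is a weakness in safety oversight that should be corrected; it is not evidence of a regulatory breach.

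**What to change.** In Appendix 2, require participating sites to send every SAE, and every death on treatment or within 30 days, to the Coordinating Center within 24 hours whatever the attribution, on the SAE form already due to the company. Keep the 10-business-day rule for non-serious events. State in 8.7 who sends the company report and whose receipt starts the FDA clock.

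Reconcile 8.6, 8.7, 10.7 and Appendix 2 on whether the DSMC receives all SAEs and all such deaths, listed by drug. A mandatory second attribution by the Study Chair would be a further preference; closing the gap does not depend on it.

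The cost is amendment wording and, where sites report to the company directly, one more recipient for an existing form. If the DSMC is to receive all of these events, its listing grows and will include deaths from progression. Appendix 2 follows a monitoring plan marked as NCI-approved, so the change may need institutional sign-off as well.

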21 CFR312

Required Regulatory Documents for Sub-sites Participating in Therapeutic UCSF Investigator Initiated Multicenter trial

Directions: Scan the documents in a zip drive and upload to OnCore.

1572

PI and Sub investigators:

- CV and Medical license
- Financial disclosure form
- NIH or CITI human subject protection training certification

Laboratories:

- CLIA &CAP and Lab Licenses
- CV and Medical License of Lab Director
- Laboratory reference ranges

Local Institutional Review Board

- IRB Approval letter
- Reviewed/Approved documents
 - Protocol version date: _____
 - Informed consent version date: _____
 - Investigator Brochure version date: _____
 - HIPAA
- Current IRB Roster

Other

- Delegation of Authority Log
 - Include NIH or CITI human subject protection training certificates or GCP training certification
- Pharmacy
 - Drug destruction SOP and Policy
- Protocol signature page
- Executed sub contract

Appendix 3 Prohibited Medications

The prohibited medications are basket-specific. Please refer to the drug-specific appendices for further information on prohibited medications.

- For patients with MET fusion to be treated with capmatinib, see Appendix 6, Section 6.11.
- For patients with ALK fusion to be treated with ceritinib, see Appendix 7, Section 7.11.
- For patients with RET or BRAF fusion to be treated with regorafenib, see Appendix 8, Section 8.11.
- For patients with NTRK1, NTRK2, NTRK3, or ROS1 fusion to be treated with entrectinib, see Appendix 9, Section 9.11.

Each drug also has specific restrictions on the use of therapeutic and prophylactic anticoagulation. These are summarized in Table X below:

Table 4. Drug-specific restrictions on anticoagulation

Study drug	Warfarin (T)	Warfarin (P)	Heparin (T)	Heparin (P)	DTI, FXa inhibitor	Low-dose ASA	Clopidogrel
Capmatinib	With caution	With caution	Permitted	Permitted	Permitted	Permitted	Permitted
Ceritinib	Not permitted	Not permitted	Permitted	Permitted	Permitted	Permitted	Permitted
Regorafenib	Not permitted	Permitted*	Not permitted	Permitted*	Permitted	Permitted	Permitted
Entrectinib	Permitted	Permitted	Permitted	Permitted	Permitted	Permitted	Permitted

T: therapeutic
 P: prophylactic
 DTI: Direct thrombin inhibitor
 FXa: Factor Xa
 Low-dose ASA: Low-dose aspirin, <=81 mg daily

* Prophylactic doses of warfarin or heparin agents resulting in PT/INR and/or PTT <=1.5 X ULN are permitted. Infrequent bleeding or elevations in PT/INR have been reported in some subjects taking warfarin while on regorafenib therapy. Therefore, subjects taking concomitant prophylactic anticoagulation should be monitored regularly for changes in PT/INR and PTT or clinical bleeding episodes.

Appendix 4 Specimen Collection

Correlative studies assessments

Tumor biopsy specimens are to be immediately immersed in formalin.

Sample shipment instructions

For each shipment, an inventory of the samples should accompany the shipment. This inventory should include the study ID, subject ID, sample number, visit number scheduled time of collection.

The original inventory will be retained at the site in the Investigator's file.

All samples will be kept at room temperature up to and during the shipment. Unless instructed otherwise, the samples will be packed carefully with suitable packing material with absorbent material in case of leakage.

All shipments should be sent by a carrier guaranteeing overnight delivery. The following items should be considered:

- Advise the carrier of the type of service desired, need for personalized door-to-door pickup, and delivery guaranteed within 24 hours.
- Advise the carrier of the nature of the shipment's contents (human biological specimens) and label the package accordingly.

Instructions for shipment of biological samples to UCSF :

[REDACTED]

[REDACTED]

[REDACTED]

[REDACTED]

[REDACTED]

[REDACTED]

[REDACTED]

[REDACTED]

Instructions for shipment (and storage) of blood samples:

[REDACTED]

[REDACTED]

[REDACTED]

[REDACTED]

[REDACTED]
